9.1 Statistical Hypotheses

No formal statistical hypothesis will be tested, as the study is designed to be exploratory.

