Appendix 8 Radiation Therapy

Radiation Target Selection

For participants in Part B, the radiation tumor target may include between 1 and 3 sites of disease excluding sites arising from the brain or spinal canal, esophagus, gastric, small bowel and must not be primary liver cancer (hepatocellular carcinoma [HCC], intrahepatic cholangiocarcinoma [ICC], mixed HCC-ICC).

In addition, the radiation tumor target per anatomical site may include a single parenchymal tumor OR a composite target including involved lymph nodes with or without an associated parenchymal tumor. Inclusion of involved lymph nodes in addition to an involved parenchymal lesion is at the discretion of the treating radiation oncologist.

The lesion or composite lesions target maximum longest diameter (inclusive of all target tumors to be irradiated) must be at least 1 cm. A maximum composite tumor target diameter is not defined; however, proposed radiation treatment plan must meet the dose constraints (at least acceptable variation) outlined in Table 22.

In the event that in the same anatomical site, multiple potential parenchymal tumor target lesions exist, in general the largest lesion should be selected unless it is necessary to select a smaller target for symptom palliation. In such cases where palliative radiation is necessary, smaller lesions likely to benefit from palliative radiation may be selected instead of the largest lesion as long as the maximum tumor diameter additive for all included tumor targets is at least 1 cm. However, for individual tumor where the longest diameter is > 5 cm, a target volume could be created within the gross tumor volume to limit the treated tumor to 5 cm. Any questions about target selection may be reviewed on a case by case basis with the Radiation Oncology Principal Investigator.

Simultaneous multisite RT is allowed. However, owing to limitations of IMRT planning, not all primary or metastatic lesions should be targeted. Three sites maximum could be selected to be irradiated provided that all selected sites could be irradiated on the same day. When selecting metastases to be irradiated, symptomatic or clinically relevant metastases could be prioritized.

Radiation Dose Specification

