Analysis of software	Many systems utilize the gamma analysis technique to compare calculations and measurements. Users typically specify the number of points that are expected to satisfy the criteria for dose (in Gy or in %) and distance (in mm) for agreements when they establish their program.
Linear accelerator for treatment delivery	The linear accelerator needs to be capable of accurately delivering intensity-modulated treatments. For Gantry-based systems using an arc delivery technique (e.g. VMAT), additional information regarding to accuracy of the gantry information at multiple delivery points need to be validated as well. For these systems, derivation of the delivery information as described for leaf sequencing above would also include verification that the gantry sequences, leaf positions, dose delivery, and time information are correct and registered (in time and MU) correctly.

Moran et al. 2011.

Gy=Grays, IMRT=Intensity-modulated Radiation Therapy, MLC=multileaf collimator, QA=quality assurance, TMS=treatment management system, TPS=treatment planning system, VMAT=volumetric modulated arc therapy.

Target Volume and Critical Structure Constraints with Compliance Criteria

Table 23 Target Volume and Critical Structure Constraints with Compliance Criteria

Structure	Dose Constraint	Acceptable Variation	Unacceptable Deviation
PTV	30 Gy ≥ 95%	30 Gy ≥ 90%	30 Gy < 90%
	Min (0.03 cc) ≥ 27 Gy	Min (0.03 cc) ≥ 25.5 Gy	Min (0.03 cc) < 25.5 Gy
	Max (0.03 cc) ≤ 36 Gy	Max (0.03 cc) ≤ 37.5 Gy	Max (0.03 cc) > 37.5 Gy
Total Parotid Glands	Mean < 17 Gy	Mean < 25 Gy	Mean > 25 Gy
Pharyngeal Constrictors	Mean < 20 Gy	Mean < 25Gy	Mean > 25 Gy
Larynx	D2cc < 30Gy	D2cc < 33Gy	D2cc > 33 Gy
	Mean < 20Gy	Mean < 25 Gy	Mean > 25 Gy
Oral mucosa	Mean < 20Gy	Mean < 25Gy	Mean > 25 Gy
Lungs	V20 Gy ≤ 20%	V20 Gy ≤ 35%	V20 Gy > 35%
	Mean ≤ 15 Gy	Mean ≤ 20 Gy	MLD > 20 Gy
Liver	> 700 cc ≤ 10 Gy	> 700 cc ≤ 18 Gy	< 700 cc ≤ 18 Gy
Spinal canal	Max (0.03 cc) ≤ 33 Gy	NA	
Heart	Max (0.03 cc) ≤ 33 Gy	Max (0.03 cc) > 36 Gy	NA
	V30 Gy ≤ 30%	V30 Gy > 30%	Min (0.03 cc) > 30 Gy
Esophagus/Stomach/Small bowel	Max (0.03 cc) ≤ 33 Gy	NA	
	V15 Gy < 10cc		
	V15 Gy < 10%	NA	V15 Gy > 10%
Brachial Plexus/Sacral Plexus/	Max (0.03 cc) < 33 Gy	Max (0.03 cc) < 36 Gy	Max > 36 Gy
Bladder	Max (0.03 cc) < 33 Gy	Max (0.03 cc) < 36 Gy	Max > 36 Gy
Total Kidney	V18 Gy < 33%	V18 Gy < 50%	V18 Gy > 50%
NonPTV	Max (1 cc) < 36 Gy	NA	

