Min = minimum, Max = maximum, NA=not applicable (the dose constraint must be met, otherwise the participant should be withdrawn), PTV=planning target volume, RT=radiotherapy.

Note: All required structures must be labeled as listed in the table below for digital RT data submission.

Documentation Requirements

As IMRT is used in this study, portal images will not be obtained, but participant-specific QA will be performed prior to the first fraction.

Cone beam CT, kV imaging, or other in-room imaging for set up is allowed.

Isodose plans for IMRT planning with dose-volume histograms of GTV, CTV, PTV, and critical structures are required.

Acceptable variations are allowed only when the geometrical arrangement of the target and critical structures is challenging. Unacceptable deviations should be avoided whenever possible and plan modifications should be attempted to improve results. The details of each radiation treatment plan

are to be collected by the study Sponsor and all acceptable variations and unacceptable deviations will be appropriately documented in the study record.

Radiation Therapy Quality Assurance Reviews

The Radiation Oncology Principal Investigator, or designee, will review all radiation treatment plans within 3 months after the study has reached the target accrual or as soon as complete data for all cases enrolled have been received. In addition, a digital record of the radiation treatment plan can be collected on a case by case basis whenever deemed necessary to be reviewed by the Sponsor and the Radiation Oncology Principal Investigator.

Radiation Therapy Adverse Events

Side effects of RT will vary depending on the location of disease, volume of normal and radiosensitive tissues in or near the radiation planning target volume. Even though, IMRT, the RT technique used in this study, may facilitate a better normal tissue sparing, all attempts should be made to minimize toxicity to surrounding healthy tissues by limiting the normal tissue radiation dose as much as possible and adhering to dose volume constraints for the main organs at risks as provided in Table 23.

Short-term or acute adverse effects occur during therapy or within 3 months after RT while long-term or late adverse effects are observed thereafter. Acute toxicities (for example mucositis) generally heal within weeks to months; late toxicities, such as fibrosis, are generally considered irreversible and progressive over time.

Potential Radiotherapy Adverse Events

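### The heart row of Table 23 contradicts itself: its acceptable-variation cells run opposite to every other row checked, leave a gap in maximum dose and set no effective limit on V30

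*Protocol*

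**What the plan says.** Under Radiation Target Selection, Appendix 8 of the protocol defines no maximum composite target diameter. It relies on the plan instead: the "proposed radiation treatment plan must meet the dose constraints (at least acceptable variation) outlined in Table 22". Table 22 lists the components of an IMRT system. The dose constraints are in Table 23.

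Table 23 gives the heart two lines:

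- Maximum dose: the Dose Constraint is "Max (0.03 cc) ≤ 33 Gy", the Acceptable Variation is "Max (0.03 cc) > 36 Gy", and the Unacceptable Deviation is NA.
- Volume: the Dose Constraint is V30 of at most 30%, the Acceptable Variation is V30 above 30%, and the Unacceptable Deviation is "Min (0.03 cc) > 30 Gy".

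The footnote defines "NA=not applicable (the dose constraint must be met, otherwise the participant should be withdrawn". The plexus and bladder rows show the usual pattern: a constraint below 33 Gy, an acceptable variation of "Max (0.03 cc) < 36 Gy", and anything above 36 Gy unacceptable.

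The Quality Assurance Reviews paragraph says that the Radiation Oncology Principal Investigator or a designee "will review all radiation treatment plans within 3 months after the study has reached the target accrual", or once all data are in. Individual plans may be collected earlier, case by case.

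**The concern.** The table is meant to tell a site whether a plan may go ahead. For the heart it gives opposing answers. By the row's own cells, 35 Gy is not acceptable and 37 Gy is. By the footnote, the same 37 Gy is a reason to withdraw the participant. A site cannot follow both.

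Thoracic targets are foreseen: exclusion criterion 17 (Section 5.2) covers them, and Table 23 has lung, heart and esophagus rows. Esophageal dose has its own exclusion criterion and its own withdrawal rule (Sections 5.2 and 7.2), and liver volume has an exclusion criterion. Heart dose has neither, so the heart row is the only place where heart dose is graded directly. Section 4.3.1 explains that M3814 is given to reduce repair of radiation-induced breaks. Appendix 8 lists cardiac toxicity among the effects of radiotherapy, and Section 2.3.2 names myocarditis as an avelumab risk.

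The general plan review may come after treatment. Section 6.6.3 lets the SMC declare late in-field toxicity a DLT, so plans accepted by inconsistent rules can also affect the Part B dose decisions.

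**Working it through.** There is no sample-size or power figure to reproduce; Section 9.1 states "No formal statistical hypothesis will be tested, as the study is designed to be exploratory". The check is a comparison of cells.

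**1. Transcription check.** Appendix 8 limits the PTV maximum to 120% of the prescribed dose, with 125% as an acceptable deviation. With 30 Gy prescribed, 1.20 × 30 = 36 Gy and 1.25 × 30 = 37.5 Gy. Both match the PTV row of Table 23, so that row was read correctly.

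**2. Direction check.** For each numeric line I compared the direction of the inequality in the Dose Constraint and Acceptable Variation columns. There are 13 lines apart from the heart: PTV coverage, minimum and maximum; parotid; pharyngeal constrictors; larynx D2cc and mean; oral mucosa; lung V20 and mean; plexus; bladder; kidney. All 13 keep the direction and move only the limit. The two heart lines are the only ones reversed.

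**3. Heart maximum, classified by the printed cells.**

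| Heart Max (0.03 cc) | Column it falls in |
|---|---|
| 30 or 33 Gy | Dose Constraint |
| 33.1, 35 or 36 Gy | none |
| 36.1, 37.5 or 45 Gy | Acceptable Variation |

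A maximum above 33 and up to 36 Gy therefore does not reach acceptable variation, while a higher one does.

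**4. Heart V30, classified by the printed cells.** Values of 0% and 30% meet the constraint; 30.1%, 60% and 100% are acceptable variation. At most 30% and above 30% together cover the whole range, so V30 alone cannot fail. The unacceptable cell grades the heart minimum. It applies only when nearly the whole heart exceeds 30 Gy, that is, when V30 is close to 100%.

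**5. The other rows that reach the heart.** Heart tissue inside the PTV falls under the PTV maximum (above 37.5 Gy is unacceptable). Heart tissue outside it falls under the NonPTV row (maximum to 1 cc below 36 Gy, with NA for variation). Both concern hot spots. As an illustration, take a heart maximum of 33 Gy, V30 of 60% and a minimum below 30 Gy. The maximum meets its constraint, V30 is labelled acceptable, the minimum cell is not triggered, and neither the PTV maximum nor the NonPTV limit is breached. No cell that applies to the heart restricts the irradiated volume here.

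**6. Could two cells have been swapped?** Exchanging the last two cells on each line would put NA under Acceptable Variation for the maximum, which could be read with the footnote. On the volume line it would make a heart minimum above 30 Gy an acceptable variation and V30 above 30% unacceptable. A heart minimum above 30 Gy implies V30 near 100%, so the same plan would be both. A swap does not repair that line.

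**The case against.** A reader might infer that the table cannot reject any plan on heart dose, or that heart dose has no ceiling. The documents do not support either reading:

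- A heart maximum above 33 and up to 36 Gy reaches neither the constraint nor the acceptable variation, so it literally fails the selection rule.
- The NA on the maximum line, by its footnote, calls for withdrawal when the constraint is missed.
- The PTV row makes more than 37.5 Gy inside the PTV unacceptable, and the NonPTV row limits the dose to 1 cc outside it. What escapes both is a small hot spot outside the PTV that leaves the 1 cc limit met.
- A failing heart condition is printed, although it uses another metric and is hard to reach.

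Other safeguards exist. Appendix 8 allows acceptable variations only where the geometry is difficult, and it requires variations and deviations to be documented, with plan details going to the sponsor. A plan accepted under this row would therefore be logged as a variation. Target-selection questions can be raised case by case. The paragraph on radiotherapy adverse events refers to Table 23 correctly, which shows which table was meant.

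The text was also read from PDF, and neighbouring rows have empty cells and a structure name that ends in a slash, so displaced cells cannot be ruled out.

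These points narrow the finding. None removes the conflict between the heart-maximum cell and the NA footnote, fills the gap above 33 and up to 36 Gy, or gives V30 a limit.

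**Conclusion.** This is an internal inconsistency in a safety-acceptance rule, not a design choice, and it is wrong as written. On the maximum line, the acceptable-variation cell is reversed, the interval above 33 and up to 36 Gy is unassigned, and the NA contradicts the neighbouring cell. On the volume line, the whole V30 range is accepted and the only unacceptable cell measures something else. The selection rule cites a table without dose constraints.

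Two limits apply. The conclusion assumes that the extracted row matches the source table, which has to be checked. And nothing in the documents shows that a thoracic target has been treated under this row, so harm to a participant should not be inferred.

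**What to change.** Check the heart row against the source table first. Then reconcile three places in Appendix 8: the target-selection rule, the heart row of Table 23, and the NA footnote. The three heart columns should be ordered, use the same metric on each line, cover the range without gaps and agree with the footnote. The radiation oncology lead sets the values; none is proposed here. Change the reference in the selection rule from Table 22 to Table 23.

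For any Part B plans already treated, check heart dose within the plan review that Appendix 8 already schedules, using the plan data that the sponsor already collects.

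The cost is one table row and one cross-reference, by amendment or clarification letter, plus one added item in an existing review. The small downside is that some thoracic plans may need re-planning.

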9.4.4 Sequence of Analyses

Interim and Additional Planned Analyses

This is an exploratory study. Available data will be evaluated during the study by the SMC.

Analyses for the Bayesian dose escalation will be performed on the DLT analysis set. Usually decisions on dose escalation will be taken once all participants of the most recent cohort have completed the DLT period or dropped out. In exceptional cases, however, the SMC may decide on the next cohort earlier, i.e. before the last participant of a cohort has finished the DLT period (considering the model recommendation and risk of overdose). Per definition of the DLT analysis set, participants who have not completed the DLT period are not included for update of the model, unless they experienced a DLT. However, such participants will be included at next SMC (if criteria for the DLT analysis set are fulfilled).

The cut off for an exploratory main analysis of the safety and preliminary antitumor activity data from the complete dose escalation will be triggered when all participants in Part A and Part B reaches the first on-treatment tumor assessment or experiences death or premature withdrawal for any reason, whichever comes first.

10 References

ACR Practice Parameter for IMRT - Revised 2016 (Resolution 40)

Berkey FJ. Managing the adverse effects of radiation therapy. Am Fam Physician. 2010;82(4):381-8,394.

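### Part B radiotherapy plans: Appendix 8 does not say plainly that a plan beyond an organ limit is not treated, and the only routine central plan review falls after accrual (minor, participant safety)

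*Protocol*

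**What the plan says.** Three parts of Protocol Appendix 8 bear on this.

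- **Radiation Target Selection** sets a mandatory floor: the "proposed radiation treatment plan must meet the dose constraints (at least acceptable variation) outlined in Table 22". Table 22 lists components of an IMRT system. The dose limits are in Table 23.
- **Documentation Requirements** is softer: "Unacceptable deviations should be avoided whenever possible and plan modifications should be attempted to improve results". The Sponsor collects the details of each plan, and both acceptable variations and unacceptable deviations are recorded. Dose-volume histograms are required for each plan, and "participant-specific QA will be performed prior to the first fraction". The footnote to Table 23 gives a firm rule, but only for cells marked NA: "the dose constraint must be met, otherwise the participant should be withdrawn".
- **Radiation Therapy Quality Assurance Reviews** places the routine review late. The person responsible, who is the Radiation Oncology Principal Investigator or someone appointed in that role's place, "will review all radiation treatment plans within 3 months after the study has reached the target accrual". The alternative trigger is complete data on every enrolled case. Earlier review is optional: "a digital record of the radiation treatment plan can be collected on a case by case basis whenever deemed necessary".

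On dose decisions, Protocol 9.4.4 gives this as the normal course: "decisions on dose escalation will be taken once all participants of the most recent cohort have completed the DLT period". Participants who drop out do not hold up the decision. Section 6.6.4 holds escalation until the SMC has decided.

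**The concern.** A site whose plan exceeds, say, a lung or kidney limit in Table 23 finds one sentence saying the plan must comply, with the wrong table number, and another that treats non-compliance as something to avoid and write down. Recording unacceptable deviations suggests that some are expected to be delivered. Nothing outside the first sentence says what happens to such a plan.

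The timing adds to this. If a planning fault did occur, no required central check would find it before the next cohort was irradiated.

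The stake is participant protection. M3814 is given shortly before each fraction because it hinders repair of radiation damage (Protocol 4.3.1), and Protocol 4.2 names a possible increase in the severity or frequency of radiation toxicity as the reason for a cautious start. Appendix 8 describes late radiation effects as generally irreversible. Compliance with normal-tissue limits is one of the main protections in Part B, so its rule should be readable in only one way.

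**Working it through.** The plan states no figure on this point, so the check is a comparison of texts, a count and a timing argument.

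**1. Which limits are affected.** Table 23 prints 21 limit lines:

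- 4 are marked NA (spinal canal; esophagus/stomach/small bowel maximum; the V15 line of less than 10% for the same group; non-PTV). These are firm stops under the footnote. Protocol 7.2 repeats the esophagus V15 stop as withdrawal before treatment.
- 1 has blank cells (V15 below 10 cc) and 2 are the heart lines. These 3 are set aside, because the table text may be damaged.
- 14 have both an acceptable-variation and an unacceptable-deviation limit: 21 − 4 − 1 − 2 = 14.

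Of these 14, 3 are PTV lines (coverage, minimum, maximum) and are not organ limits. That leaves 14 − 3 = 11 lines: parotids 1, pharyngeal constrictors 1, larynx 2, oral mucosa 1, lungs 2, liver 1, brachial/sacral plexus 1, bladder 1, kidney 1. They cover 9 structures. For these lines the only stop is the sentence with the wrong table number.

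**2. Whether another pre-treatment control covers them.** Participant-specific QA precedes the first fraction, but Table 22, which is labelled an example, describes it as verifying data transfer and dose calculation. That shows the planned dose is delivered, not that the plan respects organ limits. Dose-volume histograms hold the needed information, but no sentence requires anyone to check them against Table 23 before treatment. Sponsor collection of plan details has no stated timing and is not described as a review.

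**3. When the routine review falls relative to dose decisions.** Inputs from Protocol 6.6.4: Part B enrolls N = 6 to 24 participants, c = 3 to 6 per dose level, with a 4-week DLT period. Assume equal cohorts and one decision per cohort. There are k = N/c cohorts, and the last opens only after k − 1 decisions. So at least k − 1 of k decisions precede target accrual:

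| N | c | k | Decisions before target accrual |
|---|---|---|---|
| 24 | 6 | 4 | at least 3 of 4 |
| 24 | 3 | 8 | at least 7 of 8 |
| 6 | 3 | 2 | at least 1 of 2 |
| 6 | 6 | 1 | 0 of 1 |

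The last decision can also come first: it needs 4 weeks after the last participant starts, while the review may take up to 3 months after accrual. The accrual named is the study's, not Part B's, so Part A and Part FE could push the review later still. The alternative trigger needs data on all enrolled cases, so it does not bring the review forward to a cohort decision.

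**The case against.** The strongest reply is that the documents already lean to the strict rule. Appendix 8, in its passage on radiation adverse events, tells sites to adhere to the Table 23 constraints and names the right table. Section 8 of the protocol allows no waivers. The sentence on recording deviations can be read as bookkeeping for what cannot be avoided. All of this stands and is why the point is minor. None of it says that a plan past an organ limit is withheld, and none sets a review date.

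A second reply is that compliance data already reach the Sponsor, which holds four of the SMC's voting roles, and that the SMC Charter, the Operations Manual or the Protocol Deviation Guidance may require more. Those documents are not available. What the protocol shows is collection, not a dated review.

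A third reply is that cohort review comes after that cohort has been irradiated and helps later participants only if the fault recurs, perhaps at the same site. This is correct and limits the benefit.

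Three stronger readings are tempting and should not be drawn:

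- *That participants will be treated beyond organ limits, or that toxicity will rise.* The documents give no frequency of plan deviations.
- *That Part B dose selection is distorted.* Investigators are asked to separate causality by component (Protocol 8.2), and the SAP defines relatedness per component (15.1). Mucositis, esophagitis, radiation dermatitis and stomatitis-associated toxicity of Grade 3 or higher lasting up to 4 weeks after treatment are not DLTs (Protocol 6.6.3). All DLTs stay in the model under the fix, so its recommendation does not change.
- *That everyone after the first cohort would be protected by cohort review.* That would count order of enrollment, not protection.

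The heart row of Table 23 also reads oddly as printed, but a table-reading fault could explain it and nothing here rests on it.

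**Conclusion.** The point holds as a cheap improvement, minor in size and directed at participant safety. Two facts support it: for 11 organ-limit lines in 9 structures, Appendix 8 gives a must and a whenever-possible without saying which governs; and no plan must be centrally reviewed before the SMC decision that uses that participant's data. The timing counts assume equal cohorts and one decision per cohort. The conclusion on timing does not depend on those assumptions, because both review triggers need full enrollment. It does assume that no document outside the protocol and SAP already requires earlier review. The size of any safety gain cannot be estimated from the documents.

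**What to change.** 1. In Appendix 8, Radiation Target Selection, change the pointer from Table 22 to Table 23. In Documentation Requirements, state that a plan with an unacceptable deviation for an organ at risk is not treated, and that the treating radiation oncologist confirms this from the dose-volume histograms already required. Say also that PTV coverage or minimum-dose deviations accepted to spare an organ may be treated and documented. A blanket bar on every Table 23 deviation would block such plans and could work against safety.
2. Have the Radiation Oncology Principal Investigator or designee carry out the planned review cohort by cohort, before each Part B SMC meeting. Give the SMC the plan-compliance category (constraint met, acceptable variation, unacceptable deviation) for each participant with a DLT. Keep all DLTs in the model.

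**Cost.** The reviewer and the 6 to 24 participants' plans are the same, read 3 to 6 at a time instead of at the end. Simulation takes place at least 1 day before radiotherapy, so the 4-week DLT period is available for the review. Sites must submit plan data promptly. A few participants with difficult anatomy may be excluded, as the mandatory sentence already implies. Compliance is already to be documented; passing it to the SMC may need a small data transfer, since the DLT listing in SAP 15.2.1 draws on the adverse event page. The review protects later cohorts, not the one reviewed. Sample size and the dose model are unchanged.
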